## STUDY SYNOPSIS

Name of Sponsor/ Company:	HUYABIO International, LLC
Name of Finished Product:	HBI-8000 (tucidinostat)
Name of Active Ingredient:	N -(2-amino-4-fluorophenyl)-4-{{(2E)-3-(pyridin-3-yl)prop-2-enamido]methyl}benzamide
Title of Study:	A Phase 2 Study to Assess the Safety and Efficacy of HBI-8000 in Combination with Pembrolizumab for Advanced or Metastatic Non-Small Cell Lung Cancer (NSCLC)
Protocol No:	HBI-8000-305
Lead Investigator:	[name]
Indication	Advanced or Metastatic NSCLC
Study Population	Subjects $\geq 18$ years of age with advanced or metastatic NSCLC who have not received immune checkpoint inhibitor for their disease but have programmed death ligand 1 (PD-L1) expression Tumor Proportion Score (TPS): $\geq 1\%$ .
Study center(s):	Multicenter study (US): 6-10
Study duration:	Approximately 38 months (including follow-up)  The study will include a screening period (up to 28 days), up to 24 months of treatment of HBI-8000 with pembrolizumab, up to 1 month post-treatment follow-up for safety, and up to 12 months after the last dose of HBI-8000 for survival follow-up by telephone calls/e-mails.
Phase	2
Study Treatment	HBI-8000 tablets 30 mg/dose, orally twice a week  An HBI-8000 treatment cycle consists of twice a week dosing over 21 consecutive days. Pembrolizumab will be administered at 400 mg every 6 weeks or 200 mg every 3 weeks according to Prescribing Information and institutional practice.  Treatment will continue until disease progression or unacceptable toxicity occurs. Should toxicity be deemed not related to pembrolizumab but HBI-8000, subject may continue to receive pembrolizumab under standard of care. Should toxicities be deemed related to pembrolizumab, the subject may continue receiving HBI-8000 at the discretion of Investigator.

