### **2.3.2 Efficacy Endpoints**

Target lesion(s) and non-target lesion(s) will be assessed by imaging studies at screening (baseline assessment), in the last week of Cycle 2 including C3D1, and then every 6 weeks ( $\pm 3$  days) thereafter. Tumor assessments will follow guidelines specified in RECIST criteria v1.1.

- ORR (complete response [CR]+partial response [PR])
- DCR (CR+PR+Stable disease [SD])
- DoR
- PFS

After the discontinuation of HBI-8000 treatment, subjects without disease progression will be followed for progression with imaging of measurable disease every 12 ( $\pm 1$ ) weeks until progression, initiation of another anti-cancer treatment, or referral to hospice whichever occurs first. Survival follow-up will be performed every 12 ( $\pm 1$ ) weeks by telephone contact or e-mail for up to 12 months after the last dose of HBI-8000.

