#### **5.6      Dose Modification**

##### **5.6.1      HBI-8000 Administration**

Subjects will take 30 mg of Study Treatment orally approximately 30 minutes after a meal, beginning on Day 1 and continue every 3 to 4 days on the BIW schedule without interruption (e.g., Monday and Thursday, or Monday and Friday repeating every week).

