#### **6.1.3 Treatment Phase Assessments**

Cycle 1 Day 1: physical exam, vital signs, ECOG performance status, weight, concomitant medications, and laboratory assessments will be performed according to the Schedule of Dosing and Assessments ([Table 1](#)).

All visits and assessments from Cycle 2, Day 1 onwards may be performed  $\pm 3$  days from the date of the projected visit date. First assessment of tumor response will be scheduled on C3D1 and every 6 weeks ( $\pm 3$  days) thereafter, or sooner if a subject develops clinical signs and symptoms of disease progression, until disease progression or end of study treatment.

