### 7.2 Populations for Analyses

The following analysis sets are defined in the study for analyses of safety, efficacy, and pharmacodynamics endpoints.

**Safety Set:** Safety set consists of all enrolled subjects who received at least one dose (any amount) of Study Treatment (HBI-8000).

All safety analyses will be based on Safety Set.

**Full Analysis Set (FAS):** Full analysis set for efficacy consists of all subjects meeting eligibility criteria who receive at least one dose of HBI-8000 in combination with standard of care pembrolizumab, have at least one post-baseline assessment of efficacy, with or without imaging study.

**Per-Protocol Set (PPS):** Per-protocol set for efficacy consists of subjects meeting all eligibility criteria, having received at least 9 doses (75% of 2 cycles) of HBI-8000, with at least 1 imaging study to evaluate disease status after completing 6 weeks (2 cycles) of treatment.

Efficacy endpoints will be analyzed in both FAS and PPS.

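### The Per-Protocol Set asks for a scan after six completed weeks, but first scans may fall earlier, so some early progressors can be excluded because of their outcome

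*Combined protocol and SAP*

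**What the plan says.** Section 7.2 sets two conditions for the PPS beyond eligibility. The first is exposure: "having received at least 9 doses (75% of 2 cycles) of HBI-8000". The second is imaging: "with at least 1 imaging study to evaluate disease status after completing 6 weeks (2 cycles) of treatment".

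The timing of the first response scan is given in two ways. Section 2.3.2 and the synopsis place it "in the last week of Cycle 2 including C3D1". Section 6.1.3 says "First assessment of tumor response will be scheduled on C3D1 and every 6 weeks", with a tolerance of 3 days either side; Table 1 and its footnote q agree with Section 6.1.3. Section 6.1.3 also allows the scan "or sooner if a subject develops clinical signs and symptoms of disease progression, until disease progression or end of study treatment", and Section 6.2.1.1 lets the investigator repeat CT whenever progression is suspected.

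Footnote q ends scheduled scanning at progression. Sections 3.1.2 and 6.1.5 provide imaging after treatment only for subjects who have not progressed. Sections 7.2 and 7.5.1 analyse efficacy in both the Full Analysis Set (FAS) and the PPS, and name neither as primary.

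**The concern.** A per-protocol set should select on adherence. Here two subjects can be scanned on the same permitted day, with the same number of doses, and be treated differently according to what the scan shows. With response or stable disease, the subject is scanned again six weeks later and meets the imaging condition. With progression, the subject normally stops, has no further protocol scan, and fails it.

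At stake are the PPS estimates of objective response rate (ORR, the primary objective), disease control rate (DCR) and progression-free survival (PFS). Each early progressor removed leaves the denominator of ORR and DCR without ever having been in the numerator, and takes one of the earliest PFS events away. With 20 to 24 subjects, a few such exclusions visibly move the estimate.

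**Working it through.** **The plan's own figure.** The synopsis states: "An HBI-8000 treatment cycle consists of twice a week dosing over 21 consecutive days". Two doses a week for 3 weeks over 2 cycles is 2 × 3 × 2 = 12 doses, and 9/12 = 75%. The stated percentage reproduces.

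**Calendar.**
- Two cycles: 2 × 21 = 42 days, so Cycle 3 Day 1 is Day 43.
- First-scan window in Section 2.3.2: Days 36 to 42 plus Day 43, that is, Days 36 to 43.
- First-scan window in Section 6.1.3 and Table 1: 43 ± 3, that is, Days 40 to 46.
- Section 5.6.1 has subjects "continue every 3 to 4 days on the BIW schedule without interruption". Dosing on Days 1, 4, 8, 11, 15, 18, 22, 25, 29, 32, 36, 39 puts the 9th dose on Day 29 and the 12th on Day 39. A Monday/Friday pattern also gives Day 29 for the 9th and puts the 12th on Day 40.

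**Which scans miss the imaging condition.**
- If six weeks are complete only when Day 42 has passed, scans on Days 36 to 42 of the first window and Days 40 to 42 of the second come too early.
- If completion means the last Cycle 2 dose (Day 39 or 40), only scans before that dose miss: Days 36 to 38 or 36 to 39 of the first window. The second window then has no clear mismatch.
- An earlier scan for suspected progression misses on either reading.

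**Same day, two outcomes.** Take a scan on Day 38 in a subject with no missed doses, so at least 9 taken.
- Response or stable disease: the next scheduled scan is at Cycle 5 Day 1 (4 × 21 + 1 = Day 85, ± 3). The subject is in the PPS.
- Progression and treatment stopped: no later protocol scan. The subject is out.

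**A second route out.** A subject who progresses and stops before Day 29 has fewer than 9 doses and fails the exposure condition, whatever the scan timing.

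**Effect on ORR and DCR.** If k non-responding early progressors are removed from N and nothing else changes, each rate is multiplied by N/(N − k). The documents give no response, disease control or early-progression rate, so every count here is assumed: N = 24, 8 responders, 16 with disease control.

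| k | multiplier | ORR | DCR |
|---|---|---|---|
| 0 | 1 | 8/24 = 33.3% | 16/24 = 66.7% |
| 2 | 24/22 = 1.09 | 8/22 = 36.4% | 16/22 = 72.7% |
| 4 | 24/20 = 1.20 | 8/20 = 40.0% | 16/20 = 80.0% |

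**Effect on PFS.** As an upper bound, assume exponential PFS and exclude everyone with an event in the first 42 days (42/30.4375 = 1.38 months). The share excluded is 1 − 2^(−1.38/median): 21.3% for an assumed true median of 4 months, 14.7% for 6 months and 9.1% for 10 months. Among those left, the median is longer by 1.38 months in each case, for example 6.0 becoming 7.4 months.

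**The case against.** **Exclusion is not automatic.** Section 6.2.1.1 lets a subject with possible pseudo-progression continue to the next scan, and lets some subjects with isolated CNS progression remain on protocol. The irRECIST table in Appendix 4 asks for confirmation at least 4 weeks apart. Progression on Day 38 rescanned on Day 66 (38 + 28) or later satisfies the imaging condition. Progression first seen on Days 43 to 46 satisfies it directly. This stands: the rule affects those who progress early and stop, not all early progressors.

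**The day counts depend on a reading.** A reader might infer that most scans in the Section 2.3.2 window miss the rule, since 7 of its 8 days precede Day 43. Those are calendar days, not shares of subjects. They also take the strictest meaning of completion, and Section 6.1.3 targets Day 43 itself. This stands too, although the looser meaning still leaves Days 36 to 38 or 39 and any earlier scan.

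**The consequence is limited.** The FAS has neither the six-week scan nor the nine-dose condition, so it keeps a Day 38 progressor. The synopsis calls the analyses mainly descriptive, and no decision threshold depends on the PPS. In the illustration, the shift in ORR lies well inside the exact 95% interval for 8/24 (15.6% to 55.3%). That bounds the importance but does not remove the point: the shift has a known direction, the PPS is reported beside the FAS, and Section 7.5.1 defines ORR relative to an efficacy population that Section 7.2 does not define.

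**Detail is deferred.** Section 7 leaves methods to a SAP to be finalised before database lock. That gives an opportunity to correct the rule; it does not change the rule as written.

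**Conclusion.** The PPS imaging condition does not match the scan schedule, and applying it as written can make membership depend on outcome. The nine-dose minimum does the same for progressors who stop before about Day 29. PPS estimates of ORR, DCR and PFS may therefore be biased upward.

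The size cannot be computed from the documents. The illustrated move from 33.3% to between 36.4% and 40.0% in ORR assumes 24 subjects, 8 responders, 2 to 4 early progressors lost and no other exclusions. The PFS figures additionally assume an exponential model and loss of every early event. Other PPS exclusions, such as too few doses because of toxicity, could change the net difference from the FAS.

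A reader might infer more: that every early progressor drops out, that the PPS results are certain to be inflated, or that scan timing is the sole cause. The documents support none of these, because treatment may continue after a scan that shows progression, Days 43 to 46 qualify, and the dose minimum acts separately. Nor do they show that the trial's ORR as a whole is biased by this rule, since the FAS does not contain it. The point still deserves correction because neither set is designated primary and the repair is cheap.

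**What to change.** In Section 7.2, redefine the imaging condition as at least one tumor assessment at the first scheduled time point or later, or documented progression on any earlier scan.

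Reconcile the first-scan window so that the synopsis, Section 2.3.2, Section 6.1.3 and Table 1 with its footnote q state the same one, and tie the PPS condition to it.

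Keep the nine-dose minimum as an adherence condition, but do not let it exclude subjects whose dosing ended because of documented progression or death. Count them as non-responders in ORR, as without disease control in DCR, and as events in PFS. Changing the scan timing alone would leave this second route open.

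The cost is wording in the protocol, carried into the SAP before database lock. No extra scans or data are needed. The PPS estimates may be slightly less favourable, and the PPS will include some subjects with short exposure.

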### 7.3 Subject Disposition

The disposition of subjects will be tabulated for all enrolled subjects. Subjects who discontinue treatment or discontinued from the study will also be summarized and further broken down by reason for discontinuation.

### 7.4 Pretreatment Characteristics

Demographic and baseline characteristics will be summarized with descriptive statistics.

#### 7.4.1 Medical History

Medical histories will be coded using MedDRA (Medical Dictionary for Regulatory Activities) version 22.0 or current classification system and summarized by system organ class (SOC) and preferred term (PT) for the subjects in the safety set. For each SOC and PT, subjects with multiple events will be counted only once.

#### 7.4.2 Exposure to Study Medications

Exposure parameters to HBI-8000 and pembrolizumab will include:

- Duration of treatment of HBI-8000.
- Number of pembrolizumab administrations and dose per administration.
- Cumulative doses of HBI-8000 and pembrolizumab administered.
- Compliance to HBI-8000 administration
- Relative dose intensity (RDI) of HBI-8000 administered.

A detailed description of calculations of each of the above parameters will be provided in the SAP.

### 7.5 Statistical Analyses

#### 7.5.1 Efficacy Analyses

Efficacy analyses will be performed on FAS and PPS. ORR will be estimated based on the proportion of subjects whose best overall response is CR or PR. Disease response will be assessed using RECIST v1.1 as the primary methodology and iRECIST will be used to exclude pseudo-progression when suspected. The estimate of the ORR will be accompanied by a 2-sided

95% exact binomial confidence interval (CI). DCR (CR+PR+SD) will be analyzed similarly. DOR and PFS will be summarized descriptively using Kaplan-Meier methods. The final SAP will provide more details on these analyses.

The efficacy endpoints are the following:

- **Objective Response Rate (ORR)**, defined as the percent of subjects with CR or PR according to RECIST 1.1 and irRECIST criteria, relative to the efficacy population. Subjects who do not have an on-study assessment due to safety issues will be included as non-responders.
- **Disease Control Rate (DCR)**, defined as the percent of subjects with CR, PR or SD according to RECIST 1.1 and iRECIST criteria, relative to the efficacy population.
- **Duration of Response (DoR)**, defined as the time from documentation of tumor response to disease progression.
- **Progression-Free Survival (PFS)**, defined as the time from the start of treatment (Day 1 Cycle 1) until objective tumor progression or death.

The EoT Safety Follow-up visit is scheduled  $30 \pm 3$  days after the last dosing of the HBI-8000 or before the initiation of new cancer treatment, whichever is earlier.

Response rate endpoints (ORR, DCR) will be summarized by number and percentage of subjects meeting the definition of ORR and DCR along with the corresponding exact 95% CI based on binomial distribution.

Time-to-event endpoints (DoR, and PFS) will be summarized by Kaplan-Meier methods (median, 95% CI, number of events, number censored, and Kaplan-Meier figures).

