- b. End-of-Treatment Safety Follow-Up visit, performed 30 ± 3 days after the last day of HBI-8000 administration, or before the initiation of new cancer treatment, whichever is earlier.
- c. Informed consent must be obtained prior to initiation of any study-specific procedures.
- d. Cancer diagnosis must include known mutation status for BRAF V600, EGFR, and ALK.
- e. Temperature, heart rate, diastolic and systolic blood pressure after subject is in a supine position for at least 5 minutes.
- f. Complete physical exam at baseline. Symptom directed physical exam for screening and all other cycles.
- g. Standard 12-lead ECG will be done using local standard procedures at Baseline and at End of Treatment Safety Follow-Up visits.
- h. MRI performed per institutional guidelines and practice, and if clinically indicated for subjects with documented brain metastasis.
- i. Historical data may be used to assess for eligibility. If historical data is not available, tumor tissue will be analyzed locally by an FDA-approved test to yield PD-L1 status prior to enrollment.
- j. Hematology panel to include hemoglobin, hematocrit, red blood cell count, white blood cell count, differential, platelet count.
- k. Chemistry panel to include BUN, creatinine, AST, ALT, LDH, total bilirubin (including direct fraction if total bilirubin abnormal), lipase, amylase, TSH, T4 free (direct), total protein, albumin, uric acid, alkaline phosphatase, sodium, potassium, calcium, magnesium, phosphorus, and glucose.
- l. Urinalysis: dipstick followed by microscopic examination, if abnormal results.
- m. For women of childbearing potential (including those with tubal ligation): Serum pregnancy test at baseline (within 14 days of starting treatment) and at the end of treatment.
- n. Hepatitis B and Hepatitis C testing to include HBsAg, anti-HCV antibodies.
- o. HBI-8000 should be administered twice a week approximately 30 minutes after a meal.
- p. Pembrolizumab 400 mg every 6 weeks or 200 mg every 3 weeks on Day 1 of each Cycle should be administered as intravenous (IV) infusion over 30 minutes and in accordance with the manufacturer package insert and institutional practice.
- q. Tumor assessment of all lesions by radiographic or other modality (CT, MRI). Tumor assessments to be performed at Screening, and Day 1 of Cycles 3, 5, 7, etc. every 6 weeks (± 3 days) thereafter until PD.

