### **3.1.1      Expected Duration of Subject Participation**

Subject participation duration from screening through end of treatment visit is approximately up to 38 months, including:

Screening period:	Up to 28 days
Treatment period:	Until radiographic disease progression per RECIST v1.1 (assessed by the Investigator), unacceptable toxicity, or other reasons for discontinuation with a maximum treatment duration of 24 months, unless there is an agreement between the Sponsor and the Investigator to allow HBI-8000 beyond 24 months.
Short-term Follow up/ End of treatment (EoT) period	Up to 30 days ( $\pm 3$ days) after the last dose HBI-8000. This will be defined as EoT.
Long-term Follow-up period:	Every 12 weeks (3 months) up to a maximum of 12 months after the last dose of HBI-8000.

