#### **6.2.1.1 Tumor Response Criteria**

All measurable disease (target lesions and non-target lesions) must be documented at screening and reassessed at each subsequent tumor evaluation. Reassessment will be done by imaging studies according to RECIST Guidelines version 1.1 ([Appendix 4](#)), along with physical examinations and other methods as needed. At the Investigator's discretion, CT scans may be repeated at any time if PD is suspected.

Tumor response will be evaluated by the Investigator using the RECIST 1.1 criteria [[Eisenhauer 2009](#)] ([Appendix 4](#)) and recorded in the appropriate eCRFs. Tumor response will also be assessed centrally.

Taking into consideration possible pseudo progression, the subject may continue study treatment until the next imaging evaluation to assess tumor response according to irRECIST criteria. The same scanning modality should be used at baseline and throughout treatment for each subject.

Subjects with isolated CNS progression, but responsive/stable extracranial disease, may remain on the study protocol after consultation with Sponsor Medical Monitor.

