**Assessment of Overall Response**

Target Lesions	Non-Target Lesions	New Lesions	Overall Response
CR	CR	No	CR
CR	Non-CR/non-PD	No	PR
CR	Not evaluated	No	PR
PR	Non-PD or not all evaluated	No	PR
SD	Non-PD or not all evaluated	No	SD
Not all evaluated	Non-PD	No	Not Evaluable (NE)
PD	Any	Yes or No	PD
Any	PD	Yes or No	PD
Any	Any	Yes	PD

Source: [Eisenhauer 2009](#)

**irRECIST Summary of measurement and response assessment approaches for bidimensional and unidimensional assessment based on irRC**

**Table 1. Summary of measurement and response assessment approaches for bidimensional and unidimensional assessment based on irRC**

	Bidimensional assessment (the original irRC (7))	Unidimensional assessment
Measurable lesions	$\geq 5 \times 5 \text{ mm}^2$ by bidimensional measurements	$\geq 10 \text{ mm}$ in the longest diameter
Measurement of each lesion	The longest diameter $\times$ the longest perpendicular diameter ( $\text{cm}^2$ )	The longest diameter (cm)
The sum of the measurements	The sum of the bidimensional measurements of all target lesions and new lesions if any	The sum of the longest diameters of all target lesions and new lesions if any
Response assessment	PD: $\geq 25\%$ increase from the nadir PR: $\geq 50\%$ decrease from baseline CR: Disappearance of all lesions	PD: $\geq 20\%$ increase from the nadir PR: $\geq 30\%$ decrease from baseline CR: Disappearance of all lesions
New lesions	The presence of new lesion(s) does not define progression. The measurements of the new lesion(s) are included in the sum of the measurements.	
Confirmation	Confirmation by 2 consecutive observations not less than 4 weeks apart was required for CR, PR, and PD	

Source: [Nishino 2013](#)

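### Section 7.5.1 lets a suspected pseudo-progression be excluded but gives no rule for dating progression in PFS and DoR, and only subjects kept on treatment can have a first PD excluded or deferred

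*Combined protocol and SAP*

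**What the plan says.** **Endpoint definitions.** Section 7.5.1 has PFS run from Cycle 1 Day 1 "until objective tumor progression or death". DoR is "defined as the time from documentation of tumor response to disease progression". Neither sentence names a criterion or says which scan supplies the date. The synopsis and Section 2.3.2 list both endpoints under tumor assessments that follow RECIST 1.1, and Section 7.5.1 calls RECIST 1.1 the primary methodology. The same sentence continues: "iRECIST will be used to exclude pseudo-progression when suspected". What counts as suspected is not defined.

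**Treatment and scanning.** Section 3.1.1 sets the treatment period as "Until radiographic disease progression per RECIST v1.1 (assessed by the Investigator"), among other reasons for stopping. Section 6.2.1.1 says that, where pseudo-progression is possible, "the subject may continue study treatment until the next imaging evaluation to assess tumor response according to irRECIST criteria". Footnote q of Table 1 schedules scans "every 6 weeks (± 3 days) thereafter until PD", and Section 6.1.3 stops them at progression or at the end of study treatment. Sections 3.1.2, 6.1.5 and 6.2.1.1.2 give 12-weekly post-treatment imaging only to subjects who have not progressed.

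**Who decides.** Section 6.2.1.1.1 has the Investigator determine the progression date. The study is open-label (Section 4.3.2). Section 6.2.1.1 adds a central assessment of response, but no endpoint is tied to it.

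**Criteria.** Section 7.5.1 uses both names, iRECIST and irRECIST. Appendix 4 reproduces only the immune-related criteria labelled irRECIST, with the requirement "Confirmation by 2 consecutive observations not less than 4 weeks apart was required for CR, PR, and PD".

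**The concern.** When a first RECIST 1.1 PD is suspected to be pseudo-progression, the text allows three event dates: that first scan, the next scan, or a later PD after the first has been set aside. Two programmers could build different PFS datasets from the same scans.

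The choice is also not open for every subject. Setting a PD aside needs a later scan, and that scan depends on the Investigator's unblinded decision to continue treatment. PFS and DoR from a single-arm trial are read mainly against outside data, so a shift that can only lengthen them, in a selected subset, affects their main use. No type I error is involved, because both endpoints are secondary and descriptive.

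**Working it through.** The plan states no PFS median, event count or pseudo-progression rate, so there is no figure of its own to reproduce here. The check sets the text side by side and then sizes the gap under stated assumptions.

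**1. The two sets of criteria can disagree on the same scans (Appendix 4).**

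| | RECIST 1.1 | Appended immune-related criteria |
|---|---|---|
| New lesion | Always PD | Not PD by itself; added to the sum of measurements |
| Confirmation | Mentioned only where response is the primary endpoint | Two observations at least 4 weeks apart, for PD as well as response |

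**2. Who can have a PD reassessed.**
- *Stopped at first PD:* scheduled scans end (footnote q, Section 6.1.3). The subject has progressed, so the 12-weekly imaging does not apply. The first PD stands.
- *Kept on treatment under Section 6.2.1.1:* a further scan follows about 6 weeks later. The first PD may stand, be deferred to that scan, or be excluded.

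**3. Direction.** Let T1 be the date of the first RECIST 1.1 PD. If the clause is applied, the event falls at T1 (PD stands and is dated back), at T1 + 6 weeks (dated at the next scan), or at a later PD, death or censoring date (PD excluded). The result is never earlier than T1.

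**4. Size (illustration only).** Inputs:
- n = 24, the upper planned size (Section 7.1).
- Scan interval 6 weeks (footnote q): 42 / 30.44 = 1.38 months.
- True median PFS assumed at 6.0 months, and at 8.8 months. The second is the PFS median of the pembrolizumab-plus-chemotherapy arm described in Section 1.1.1, a different regimen, used only as a scale.
- Exponential progression times rounded up to the next scan; no deaths or censoring; 20,000 simulated trials per setting.

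With every event dated at T1, the standard deviation of the sample median is about 1.8 months (true median 6.0) and 2.6 months (8.8).

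*Deferral:* a fraction f of events becomes T1 + 1.38 months. The mean rise in the median is much the same for both true medians:

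| f | Rise, months |
|---|---|
| 10% | 0.15 |
| 25% | 0.37 |
| 50% | 0.7 |
| 100% | 1.38 (every event moves one interval) |

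*Exclusion:* a fraction e of first PDs is removed. The next PD comes either two scans later (T1 + 2 × 1.38 = T1 + 2.76 months) or after a fresh exponential time with the same median. The mean rise in the median, in months, is:

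| e | Two scans later, 6.0 / 8.8 | Fresh exponential, 6.0 / 8.8 |
|---|---|---|
| 5% | 0.16 / 0.15 | 0.35 / 0.5 |
| 10% | 0.32 / 0.30 | 0.7 / 1.0 |
| 20% | 0.62 / 0.6 | 1.5 / 2.2 |

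Against the standard error, 50% deferral is 0.7 / 1.8 = 0.39 at the 6.0-month median. The largest exclusion cell is 2.2 / 2.6 = 0.85.

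**5. Effect of the fix.** With first-PD dating for everyone, the shift is zero by construction.

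**The case against.** The strongest reply is that RECIST 1.1 already governs. The synopsis and Section 2.3.2 place PFS and DoR under it, and Section 7.5.1 calls it primary. In the definitions of Section 7.5.1, only ORR and DCR add the immune-related criteria. The exclusion clause has disease response as its subject and sits among the ORR sentences. This is the more natural reading, and it stands as far as it goes. But progression is what the clause excludes, and no dating sentence settles the matter.

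Second, the final SAP is to give more detail, and dating rules could sit there. That is possible. However, Section 7 requires the SAP only before database lock, so in an open-label study the rule could be chosen with outcomes known.

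Third, there is a central read. It would limit the problem if it supplied the PFS and DoR dates, but nothing says that it does.

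Three stronger readings are tempting, and the documents do not support them:
- *That PFS will be biased upward by a known amount.* The documents give no rate of suspected or excluded PD and do not prescribe next-scan dating. If a confirmed PD is dated back to its first scan, it causes no shift.
- *That any such lengthening is unrelated to the drug.* Where a later scan shows that the first PD was not progression, setting it aside is what the immune-related criteria intend.
- *That a subject responding after an excluded PD has no DoR end date.* If RECIST 1.1 governs, that subject is not counted as a responder and does not enter DoR. This turns on the response criterion, a separate question.

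**Conclusion.** The concern holds as a gap in the definition. The text leans to RECIST 1.1 for PFS and DoR, yet it contains a clause that can remove a PD and no rule for dating the event. The scan schedule makes that removal possible only for subjects kept on treatment by unblinded judgement. If the clause is applied to these endpoints, the dates can only stay or move later.

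The size cannot be established from the documents. Under the assumptions above, the rise in median PFS runs from about 0.15 months (10% deferred, or 5% excluded with the next PD two scans later) to 2.2 months (20% excluded, fresh exponential time, true median 8.8). Every case shown is below one standard error of a median from 24 subjects. DoR is exposed in the same way but was not simulated. The point is worth correcting because the change is small and the shift, if any, runs one way.

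**What to change.** In Section 7.5.1, add a sentence to this effect: *For PFS and DoR, progression is the first RECIST 1.1 PD, dated at the scan that first shows it, whether or not treatment continues and whether or not a later scan is judged non-PD under the immune-related criteria.* Then:

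- State whether the Investigator or the central read supplies the date.
- Limit the pseudo-progression clause to a supportive immune-related analysis of PFS and DoR with its own dating rule, and use one named criterion throughout.
- Align footnote q of Table 1 and Section 6.1.3 with the follow-up scan that Section 6.2.1.1 already foresees, so that the supportive analysis can be scored.
- Sections 3.1.1 and 6.2.1.1 differ on treatment past a RECIST 1.1 PD. The sponsor must reconcile them; no treatment rule is proposed here.

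The cost is wording in the protocol and SAP. It adds no scans beyond those Section 6.2.1.1 foresees. The downside is that reported PFS and DoR may be slightly shorter.
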